7.1.2. Durvalumab

Durvalumab (MEDI4736) will be supplied by AstraZeneca as a 500-mg vial solution for infusion after dilution. The solution contains 50 mg/mL durvalumab, 26mM histidine/histidine hydrochloride, 275mM trehalose dihydrate, and 0.02% (weight/volume [w/v]) polysorbate 80; it has a pH of 6.0. The nominal fill volume is 10 mL.

Investigational product vials are stored at 2°C to 8°C (36°F to 46°F) and must not be frozen. Durvalumab must be used within the individually assigned expiry date on the label.

The following applies to the preparation of durvalumab doses for administration with an I.V. bag. The dose for administration must be prepared by the investigator's or the site's designated investigational product manager using aseptic technique. Total time from needle puncture of the durvalumab vial to the start of administration should not exceed:

- 24 hours at 2°C to 8°C (36°F to 46°F)
- 4 hours at room temperature

If in-use storage time exceeds these limits, a new dose must be prepared from new vials. Infusion solutions must be allowed to equilibrate to room temperature prior to commencement of administration.

Refer to [Attachment 9](#) for the durvalumab dose volume calculation.

7.1.3. *Tremelimumab*

Tremelimumab will be supplied by AstraZeneca as a 20-mg/mL solution for infusion after dilution. The solution contains 20 mg/mL of tremelimumab, 20mM histidine/histidine hydrochloride, 222mM trehalose dihydrate, 0.02% (w/v) polysorbate 80, and 0.27mM disodium edetate dihydrate (EDTA); it has a pH of 5.5. The nominal fill volume is 20 mL. Investigational product vials are stored at 2°C to 8°C (36°F to 46°F) and must not be frozen. Tremelimumab must be used within the individually assigned expiry date on the label.

The following applies to the preparation of tremelimumab doses for administration with an I.V. bag. The dose of tremelimumab for administration must be prepared by the investigator's or the site's designated investigational product manager using aseptic technique. Total time from needle puncture of the tremelimumab vial to the start of administration should not exceed:

- 24 hours at 2°C to 8°C (36°F to 46°F)
- 4 hours at room temperature

It is recommended that the prepared final I.V. bag be stored in the dark at 2°C to 8°C (36°F to 46°F) until needed. If storage time exceeds these limits, a new dose must be prepared from new vials. The refrigerated infusion solutions in the prepared final I.V. bag should be equilibrated at room temperature for about 2 hours prior to administration. Tremelimumab does not contain preservatives and any unused portion must be discarded.

No incompatibilities between tremelimumab and polyvinylchloride or polyolefin I.V. bags have been observed.

Refer to [Attachment 9](#) for the tremelimumab dose volume calculation.

7.2. Study Drug Administration

The investigator or designee is responsible for:

- explaining the correct use of the investigational agent(s) and planned duration of each individual's treatment to the site personnel
- verifying that instructions are followed properly
- maintaining accurate records of study drug dispensation, and collection, and returning or destroying all unused medication to Lilly or its designee at the end of the study.

Patients will be instructed to contact the investigator as soon as possible if they have a complaint or problem with the study drug(s) so that the situation can be assessed.

7.2.1. Dosing Schedule

Refer to Section [7.2.2](#) for Part A (dose escalation) dose regimens for each combination, by cohort. Refer to Section [7.2.3](#) for Part B (disease-specific expansion) dose regimens for LY3022855-plus-durvalumab, by cohort.

For each combination regimen, LY3022855 will be administered first, followed by a 30-minute observation period. After the observation period, durvalumab or tremelimumab will be administered. In this study, a cycle is defined as 4 weeks (28 days); Day 1 of a cycle is based on the administration of LY3022855 (rather than durvalumab or tremelimumab). A delay of study treatment due to holiday, weekend, bad weather, or other unforeseen circumstances will be permitted for a maximum of 3 days and not counted as a protocol deviation.

7.2.1.1. LY3022855

Eligible patients will receive LY3022855 as an I.V. infusion administered over a minimum duration of 30 minutes and a maximum duration of 4 hours, based on the known safety and stability of the prepared drug. The infusion rate should not exceed 25 mg/minute. Suggested infusion times are as follows:

- 90 minutes for the first infusion; if no infusion-related reaction (IRR) is observed, decrease the infusion time to 60 minutes for the second infusion
- 60 minutes for the second infusion; if no IRR is observed, decrease the infusion time to 30 minutes for the third infusion
- 30 minutes for the third and subsequent infusions

If, at any time, a patient experiences an IRR, the infusion time should not be decreased.

Premedication is not recommended to be administered prior to the first infusion of LY3022855. However, if the patient experiences a Grade 1 or 2 IRR, premedication must be provided prior to any subsequent doses of LY3022855. The choice of premedication is to be made after discussion and agreement between the investigator and sponsor. In such cases (Grade 1 or 2 IRRs), administration of steroids should be avoided, if possible. If an IRR Grade ≤ 2 occurs during or after LY3022855 administration and the patient's condition allows it, treatment with durvalumab or tremelimumab will proceed as planned. Patients experiencing an IRR Grade ≥ 3 will be permanently discontinued from study treatment.

LY3022855 may be administered up to 3 days AFTER the scheduled dosing date and up to 4 days BEFORE the next scheduled dosing date to accommodate for patient vacations, holidays, inclement weather or other unforeseen circumstances. If, at any time, a dose is to be administered beyond the 3-day window, that dose is to be skipped. A maximum of 28 days between administered doses is allowed for delays due to adverse events.

7.2.1.2. Durvalumab

Patients are to receive durvalumab I.V. on Days 1 and 15 of every cycle. Durvalumab may be administered up to 3 days AFTER the scheduled dosing date. If, at any time, a dose is administered beyond the 3-day window, that dose is considered a dose delay. A maximum delay of 28 days between administered doses is allowed (for dose delay in case of immune-related AE

please refer to Section 7.2.4.1). Note that a maximum of 12 months/26 doses of durvalumab treatment is permitted.

Refer to [Attachment 9](#) for the durvalumab dose volume calculation.

Durvalumab will be administered at room temperature (approximately 25°C) by controlled infusion via an infusion pump into a peripheral or central vein. Following preparation of durvalumab, the entire contents of the I.V. bag should be administered as an I.V. infusion over approximately 60 minutes (± 5 minutes), using a 0.2- or 0.22- μ m in-line filter. Less than 55 minutes is considered a deviation.

The I.V. line will be flushed with a volume of I.V. solution (0.9% [w/v] saline) equal to the priming volume of the infusion set used after the contents of the I.V. bag are fully administered, or complete the infusion according to institutional policy to ensure the full dose is administered and document if the line was not flushed.

A 1-hour observation period is required after the first infusion of durvalumab. If no clinically significant infusion reactions are observed during or after the first cycle, subsequent infusion observation periods can be at the investigator's discretion (suggested 30 minutes after each durvalumab infusion).

Patients will be monitored during and after the infusion with assessment of vital signs at the times specified in this study protocol.

In the event of a Grade ≤ 2 IRR, the infusion rate of study drug may be decreased by 50% or interrupted until resolution of the event and re-initiated at 50% of the initial rate until completion of the infusion. For patients with a Grade ≤ 2 IRR, subsequent infusions may be administered at 50% of the initial rate. Acetaminophen and/or an antihistamine (for example, diphenhydramine) or equivalent medications per institutional standard may be administered at the discretion of the investigator. If the IRR is Grade ≥ 3 in severity, study drug will be permanently discontinued.

7.2.1.3. Tremelimumab

Patients are to receive tremelimumab I.V. on Day 1 of every cycle for the first 6 doses (Cycles 1-6). Starting with Cycle 7 (4 weeks after Dose 6 [Week 25]), tremelimumab will be dosed once every 3 cycles (12 weeks), that is, on Day 1 of Cycles 7, 10, 13, and so on, until disease progression.

Tremelimumab may be administered up to 3 days AFTER the scheduled dosing date. If, at any time, a dose is administered beyond the 3-day window, that dose is considered a dose delay. A delay of up to 28 days between administered doses is allowed for Cycles 1 through 6, and up to 60 days between doses for Cycles 7 and beyond.

Refer to [Attachment 9](#) for the tremelimumab dose volume calculation.

Tremelimumab will be administered at room temperature (approximately 25°C) by controlled infusion via an infusion pump into a peripheral or central vein. Following preparation of tremelimumab, the entire contents of the I.V. bag should be administered as an I.V. infusion over

approximately 60 minutes (± 5 minutes), using a 0.2- or 0.22- μm in-line filter. Less than 55 minutes is considered a deviation.

The I.V. line will be flushed with a volume of 0.9% (w/v) saline equal to the priming volume of the infusion set used after the contents of the I.V. bag are fully administered, or complete the infusion according to institutional policy to ensure the full dose is administered and document if the line was not flushed.

In the event that either preparation time or infusion time exceeds the time limits presented in this section, a new dose must be prepared from new vials. Tremelimumab does not contain preservatives, and any unused portion must be discarded.

A 1-hour observation period is required after the first infusion of tremelimumab. If no clinically significant infusion reactions are observed during or after the first cycle, subsequent infusion observation periods can be at the investigator's discretion (suggested 30 minutes after each tremelimumab infusion).

Patients will be monitored during and after the infusion with assessment of vital signs at the times specified in this study protocol.

In the event of a Grade ≤ 2 IRR, the infusion rate of study drug may be decreased by 50% or interrupted until resolution of the event and re-initiated at 50% of the initial rate until completion of the infusion. For patients with a Grade ≤ 2 IRR, subsequent infusions may be administered at 50% of the initial rate. Acetaminophen and/or an antihistamine (for example, diphenhydramine) or equivalent medications per institutional standard may be administered at the discretion of the investigator. If the IRR is Grade ≥ 3 in severity, study drug will be permanently discontinued.

As with any antibody, allergic reactions to dose administration are possible. Appropriate drugs and medical equipment to treat acute anaphylactic reactions must be immediately available, and study personnel must be trained to recognize and treat anaphylaxis. The study site must have immediate access to emergency resuscitation teams and equipment in addition to the ability to admit patients to an intensive care unit if necessary.

7.2.2. Part A: Dose Escalation (Phase 1a)

By nature of being a dose-escalation study, data will be evaluated on an ongoing basis until the MTD is determined. Safety data, in particular AEs, will be the primary criteria for the dose escalation. No dose escalation can occur without prior discussion and agreement between the investigator, the Lilly study team, and the collaborator; the decision will be documented in writing.

Based on the ongoing safety reviews, modifications to the dose-escalation strategy or other design elements may be made via protocol amendment to ensure patient safety. No intrapatient dose escalation is permitted for any patient. Dose escalation may be ceased at any time based on available safety and PK behavior.

In Part A, study drugs for the LY3022855-plus-durvalumab and LY3022855-plus-tremelimumab combinations may be administered at the dose regimens shown in [Table JSCC.1](#) and

Table JSCC.2, respectively. Refer to Section 7.2.2.2 for further details on the planned dose-escalation method, proceeding from Cohorts D1a and T1a.

Table JSCC.1. Part A (Dose Escalation) Dose Regimens for the LY3022855-plus-Durvalumab Combination, by Cohort

Cohort	LY3022855		Durvalumab	
	Dose (mg)	Frequency	Dose (mg)	Frequency
D1a	25	QW	750	Q2W
	D1b ^a	25 Days 1, 8, and 15 of each cycle	750	Q2W
	D1c	25 Q2W	750	Q2W
D2a	50	QW	750	Q2W
	D2b ^a	50 Days 1, 8, and 15 of each cycle	750	Q2W
	D2c	50 Q2W	750	Q2W
D3a	75	QW	750	Q2W
	D3b ^a	75 Days 1, 8, and 15 of each cycle	750	Q2W
	D3c	75 Q2W	750	Q2W
D4a	100	QW	750	Q2W
	D4b ^a	100 Days 1, 8, and 15 of each cycle	750	Q2W
	D4c	100 Q2W	750	Q2W

Abbreviations: QW = weekly; Q2W = every 2 weeks.

Note: A cycle is defined as 28 days (4 weeks). QW refers to dosing on Days 1, 8, 15, and 22 of each cycle; Q2W refers to dosing on Days 1 and 15 of each cycle.

^a Enrollment to the Dnb cohort will occur only if ≥ 2 DLTs are observed after Cycle 1, Day 21 of the corresponding Dna cohort.

Table JSCC.2. Part A (Dose Escalation) Dose Regimens for the LY3022855-plus-Tremelimumab Combination, by Cohort

Cohort	LY3022855		Tremelimumab	
	Dose (mg)	Frequency	Dose (mg)	Frequency ^a
T1a	50	QW	75	Q4W
	T1b ^b	50 Days 1, 8, and 15 of each cycle	75	Q4W
	T1c	50 Q2W	75	Q4W
T2a	100	QW	75	Q4W
	T2b ^b	100 Days 1, 8, and 15 of each cycle	75	Q4W
	T2c	75 Q2W	75	Q4W
T3a	100	QW	225	Q4W
	T3b ^b	100 Days 1, 8, and 15 of each cycle	225	Q4W
	T3c	100 Q2W	225	Q4W
	T3d	75 QW	225	Q4W
T4a	100	QW	750	Q4W
	T4b	100 Q2W	750	Q4W
	T4c	100 Days 1, 8, 15 of each cycle	750	Q4W
	T4d	75 QW	750	Q4W

Abbreviations: QW = weekly; Q2W = every 2 weeks; Q4W = every 4 weeks.

Note: A cycle is defined as 28 days (4 weeks). QW refers to dosing on Days 1, 8, 15, and 22 of each cycle; Q2W refers to dosing on Days 1 and 15 of each cycle; Q4W refers to dosing on Day 1 of each cycle.

^a After 6 doses, tremelimumab to be dosed once every 12 weeks until discontinuation.

^b Enrollment to the Tnb cohort will occur only if ≥ 2 DLTs are observed after Cycle 1, Day 21 of the corresponding Tna cohort.

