Therefore, based on the available clinical PK, pharmacodynamic, and safety data collected for LY3022855 in Study JSCA and Study JSCB, and considering the lack of clinical experience with LY3022855 in combination with other drug treatments, dose escalation of LY3022855 will commence at an initial dose level of 25 mg QW (approximately equivalent to a 0.3-mg/kg QW dose in a 75-kg patient) when in combination with durvalumab. This LY3022855 dose was not associated with any DLTs in the JSCA monotherapy dose-escalation trial and is approximately one fourth of the currently recommended Phase 2 dose of LY3022855 (1.25 mg/kg Q2W). Because the planned dose of durvalumab is equal to the dose being used in Phase 3 studies and because there is no planned dose escalation of durvalumab, a slightly lower LY3022855 starting dose was selected for the combination with durvalumab, compared with that selected for the combination with tremelimumab. Dose escalation of LY3022855 in combination with

durvalumab will proceed in 25-mg increments, up to a planned maximum of 100 mg QW (approximately equivalent to a 1.25-mg/kg QW dose in a 75-kg patient).

Dose escalation of LY3022855 when in combination with tremelimumab will commence at an initial dose level of 50 mg QW (approximately equivalent to a 0.6-mg/kg QW dose in a 75-kg patient). This LY3022855 dose was not associated with any DLTs in the JSCA monotherapy dose-escalation trial and is approximately one half of the currently recommended Phase 2 dose of LY3022855 (1.25 mg/kg Q2W). Because the planned starting dose of tremelimumab is approximately one tenth of the dose being used in Phase 3 studies and because there is a planned dose escalation for tremelimumab, a slightly higher LY3022855 starting dose was selected for the combination with tremelimumab, compared with that selected for the combination with durvalumab. Dose escalation of LY3022855 in combination with tremelimumab will proceed as a single 50-mg increment, up to a planned maximum of 100 mg QW (approximately equivalent to a 1.25-mg/kg QW dose in a 75-kg patient).

Furthermore, in the case where unacceptable toxicity is observed for the continuous dosing schedule (that is, once per week), the impact of either a reduced dose or a reduced dosing intensity (that is, a weeklong break in treatment) on patient safety will be evaluated.

Abbreviations: PK = pharmacokinetic(s); QW = weekly; Q2W = every 2 weeks.

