5.4.3. Tremelimumab

As of November 2014, approximately 973 patients have received I.V. tremelimumab monotherapy.

Following an initial multiple-dose escalation of tremelimumab (3, 6, 10 mg/kg every 28 days [Q28D]) in a Phase 1/2 study (Study A3671002), patients were subsequently enrolled to evaluate the antitumor activity of 2 alternative dosing regimens: 10 mg/kg I.V. Q28D versus 15 mg/kg I.V. every 90 days (Q90D). Among patients treated with 10 mg/kg Q28D or 15 mg/kg Q90D, the median durations of objective response were 553 days and 722 days, respectively.

Treatment-related SAEs occurred in 25.0% of patients treated with 10 mg/kg Q28D and in 8.9% of patients treated with 15 mg/kg Q90D. The results of this study led to a decision to proceed with the dosing regimen of 15 mg/kg Q90D in subsequent studies initiated by Pfizer Inc (previous sponsor).

However, subsequent retrospective exposure-response analyses suggested that the 15-mg/kg Q90D schedule could result in underexposure to tremelimumab. An intensified schedule of tremelimumab is now under evaluation whereby patients receive 10 mg/kg Q28D for 6 doses, followed by 15 mg/kg Q90D until treatment discontinuation (Calabro et al. 2015).

In the ongoing combination study with durvalumab and tremelimumab (Study D4190C00006), the dose level selected for tremelimumab in the dose-expansion phase is 1 mg/kg Q4W. Doses higher than 1 mg/kg Q4W (that is, 3 mg/kg Q4W and 10 mg/kg Q4W) in combination with durvalumab at 10, 15, or 20 mg/kg Q4W were associated with increased incidence of AEs.

A population PK model was developed for tremelimumab using data from Phase 1 through Phase 3 studies (N=654; 0.01-15-mg/kg doses Q4W or Q90D; metastatic melanoma) (Wang et al. 2014). The population PK model indicated minor impact of body weight on PK of tremelimumab (coefficient of ≤ 0.5). The weight-based (1 mg/kg Q4W) and fixed-dosing (75 mg Q4W; based on median body weight of approximately 75 kg) regimens were compared using predicted PK concentrations (5th, median, and 95th percentiles) using the population PK model in a simulated population of 1000 patients with body weight distribution of 40 to 120 kg. Similar to durvalumab, simulations indicated that both body weight-based and fixed-dosing regimens of tremelimumab yield similar median steady-state PK concentrations with slightly less between-subject variability with the fixed-dosing regimen.

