7.2.2.2. Dose-Escalation Method

Three to 6 patients will be enrolled to Cohort 1a (that is, Cohort D1a or T1a; refer to [Table JSCC.1](#) and [Table JSCC.2](#) for LY3022855-plus-durvalumab and LY3022855-plus-tremelimumab combinations, respectively). If none of the first 3 patients or 1 of 6 patients in Cohort 1a experiences a DLT event, enrollment to the next “a” cohort will proceed (that is, to Cohort 2a, and so on). However, if 1 of 3 patients in any cohort (that is, at any dose level) experiences a DLT, up to 3 additional patients will be enrolled at that dose level. If a DLT is observed in ≥ 2 of a maximum of 6 patients in Cohorts 1a, 2a, 3a, or 4a, concurrent enrollment of 3 to 6 patients to each of the respective “b”, “c”, and “d” cohorts (as applicable) will occur and no higher dosages will be explored. For example, if no DLTs are noted in Cohort 1a, enrollment to Cohort 2a will occur; however, if 2 patients in Cohort 2a experience DLTs, enrollment to Cohorts 2b and 2c will occur concurrently and no higher dosages will be studied. An exception to this method is that enrollment to Dnb/Tnb cohorts will occur only if ≥ 2 DLTs are observed after Cycle 1, Day 21 of the corresponding Dna/Tna cohorts. All patients will be assigned to treatment cohorts by the sponsor, with patients assigned sequentially to the “b”, “c”, and “d” cohorts.

The MTD identified for each combination therapy in Part A will then be the dosage used (confirmed) in Part B (Phase 1b/disease-specific expansion). However, if each of the “b”, “c”, and “d” cohorts (as applicable) in Part A are observed to have a probability of causing a DLT that is lower than 33%, the sponsor (in consultation with the collaborator) will select the dosage to be used in Part B, based on clinical or correlative study results.

Table JSCC.3. MTD Determination for the Combination of LY3022855 plus Durvalumab

Cohort	Number of Patients Who Experience a DLT (in Cycle 1)		
	0 of 3	1 of 6	≥2
D1a D1b D1c	Enroll to D2a MTD is D1b MTD is D1c	Enroll to D2a MTD is D1b MTD is D1c	Enroll to D1b and D1c Not defined Not defined
D2a D2b D2c	Enroll to D3a MTD is D2b MTD is D2c	Enroll to D3a MTD is D2b MTD is D2c	Enroll to D2b and D2c MTD is D1a MTD is D1a
D3a D3b D3c	Enroll to D4a MTD is D3b MTD is D3c	Enroll to D4a MTD is D3b MTD is D3c	Enroll to D3b and D3c MTD is D2a MTD is D2a
D4a D4b D4c	MTD is D4a MTD is D4b MTD is D4c	MTD is D4a MTD is D4b MTD is D4c	Enroll to D4b and D4c MTD is D3a MTD is D3a

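### At dose level T4 the "b" and "c" schedules are swapped and carry no footnote, so the after-Day-21 condition never applies to the Days 1/8/15 cohort (minor)

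*Protocol*

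**What the plan says.** Protocol Section 7.2.2, Tables JSCC.1 and JSCC.2, lists the Part A cohorts; the synopsis repeats both tables. At D1 to D4 and T1 to T3, the "b" cohort receives LY3022855 on Days 1, 8 and 15 and carries a footnote mark. T2b and T3b, for example, read "100 Days 1, 8, and 15 of each cycle". For the tremelimumab arm the footnote begins "Enrollment to the Tnb cohort will occur only if" and requires at least 2 DLTs after Cycle 1 Day 21 of the matching "a" cohort.

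At T4 the rows differ. T4b is 100 mg Q2W, T4c is "100 Days 1, 8, 15 of each cycle", and neither row has the mark. Both copies of the table agree.

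Section 7.2.2.2 gives the default after 2 or more DLTs in an "a" cohort: "concurrent enrollment of 3 to 6 patients to each of the respective" "b", "c" and "d" cohorts. It then limits this: "An exception to this method is that enrollment to Dnb/Tnb cohorts will occur only if" the same late-DLT condition is met. The limit is tied to the letter b, not to the schedule. Nothing else in the protocol or SAP restricts T4c.

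**The concern.** The condition suits the Days 1/8/15 schedule. That schedule differs from weekly dosing only by omitting Day 22, so it can help only with toxicity that arises after Day 21. If the DLTs came earlier, new patients would get the same treatment over the period in which the DLTs occurred. The condition prevents this at seven levels and fails to at T4.

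The two statements of the condition also disagree about T4b. By letter (Section 7.2.2.2), early DLTs in T4a shut T4b, the less intense Q2W schedule. By footnote mark, T4b opens. On either reading T4c opens. At stake is a written enrolment rule that sends 3 to 6 patients to a regimen unchanged over the window of concern.

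**Working it through.** **The plan's own figure.** Section 10.1 gives 12 to 42 patients for the tremelimumab combination and 78 for Part A. These reproduce:
- tremelimumab minimum 4 × 3 = 12; maximum 4 × 6 + 3 × 6 = 42
- durvalumab maximum 4 × 6 + 2 × 6 = 36
- total 42 + 36 = 78

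**Exposure through Day 21.** From the table notes, QW is Days 1, 8, 15 and 22, Q2W is Days 1 and 15, and tremelimumab Q4W is Day 1.

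| Cohort | LY3022855 through Day 21 | Tremelimumab |
|---|---|---|
| T4a (100 mg QW) | 3 × 100 = 300 mg | 750 mg |
| T4b (100 mg Q2W) | 2 × 100 = 200 mg | 750 mg |
| T4c (100 mg Days 1/8/15) | 3 × 100 = 300 mg | 750 mg |
| T4d (75 mg QW) | 3 × 75 = 225 mg | 750 mg |

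T4a and T4c match in dose and dosing days until Day 22.

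**Cohorts opened when T4a has 2 or more DLTs by Day 21 and fewer than 2 later.**
- By letter: T4c and T4d open; T4b (Q2W) stays shut.
- By footnote mark: T4b, T4c and T4d all open.
- With the labels corrected: Q2W and T4d open; Days 1/8/15 stays shut.

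**How often this would matter.** The documents give no DLT rate or timing, so both are assumed. Let p be the Cycle 1 DLT rate in T4a and s the share of DLTs after Day 21. Under 3+3, P(T4a fails) = 1 − [(1−p)³ + 3p(1−p)⁵]. Given failure with k DLTs, the late count is taken as Binomial(k, s).

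| | p = 0.20 | 0.33 | 0.40 | 0.50 |
|---|---|---|---|---|
| Fewer than 2 late DLTs, s = 0.10 | 0.987 | 0.985 | 0.983 | 0.982 |
| s = 0.25 | 0.921 | 0.910 | 0.904 | 0.896 |
| s = 0.50 | 0.707 | 0.679 | 0.664 | 0.645 |
| 2 or more DLTs by Day 21, s = 0.10 | 0.837 | 0.853 | 0.862 | 0.873 |
| s = 0.25 | 0.610 | 0.640 | 0.655 | 0.675 |
| s = 0.50 | 0.293 | 0.321 | 0.336 | 0.355 |

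The upper block is how often the usual condition would keep Days 1/8/15 shut: 65-99% of failures. The lower block is how often T4c repeats the exposure that preceded at least two of the DLTs: 29-87%. Even onset over 28 days gives s = 7/28 = 0.25, hence 90-92% and 61-68%.

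**Gross risk in T4c.** Here p is the DLT rate by Day 21, assumed 20-50%. P(2 or more DLTs) runs from 0.291 to 0.828. Expected enrolment, 3 + 9p(1−p)², is 4.1 to 4.3 patients, and expected DLTs, p times that, are 0.8 to 2.1.

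**Net of Q2W.** On the by-letter reading T4c runs where Q2W should. Suppose Q2W lowers the DLT rate by d, with p = 0.20 to 0.50.
- d = 0: no difference.
- d = 0.05: 0.16-0.24 fewer DLTs, and 6-11 points off P(2 or more).
- d = 0.10: 0.34-0.47 fewer DLTs, and 14-21 points off.

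On the by-mark reading, T4c is an extra cohort of 3 to 6 patients instead of a substitute for Q2W.

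**The case against.** The strongest objection is about cause. T4a differs from T3a only in tremelimumab, 750 mg against 225 mg, and LY3022855 100 mg QW must already have passed at T2a and T3a. New DLTs at T4a would most plausibly come from the higher tremelimumab dose or its interaction with LY3022855. Every T4 cohort gives that dose on Day 1, so relabelling changes only LY3022855 timing. This stands, and it is why the net figure starts at zero.

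A reader might infer that the 29-83% chance of 2 or more DLTs is harm caused by the swap. The documents do not support that: the rates are assumed, and much of the risk could remain under Q2W or T4d. Section 5.4.3 reports "Treatment-related SAEs occurred in 25.0% of patients treated with 10 mg/kg Q28D" (750 mg in a 75-kg patient), but those events are not DLTs and are not confined to Cycle 1. A reader might also take 90-92% as the share of failures in which patients repeat the regimen that produced the DLTs. It is the share in which the usual condition would stay shut, and it includes failures with one early and one late DLT.

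Section 5.4.1 says that, if weekly dosing is too toxic, the impact of a reduced dose or "a reduced dosing intensity (that is, a weeklong break in treatment) on patient safety will be evaluated", with no late-DLT condition. Opening T4c fits that general rationale. But the condition was added in Section 7.2.2.2 and the footnotes, and no text explains a different order or a dropped condition at T4.

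Controls exist: the sponsor assigns each patient, data are reviewed cohort by cohort, and "Dose escalation may be ceased at any time based on available safety and PK behavior". They make a mechanical repeat unlikely, but they do not correct the rule. The requirement for prior agreement concerns escalation, and opening T4c after T4a fails is not an escalation.

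**Conclusion.** The inconsistency is real and appears in both copies of the table. As written, 2 or more DLTs by Day 21 in T4a open T4c, which is the same as T4a through Day 21; read by letter, the rule also shuts the less intense Q2W cohort. On the assumed rates and timing, and with late DLTs treated as independent, the condition used elsewhere would have stayed shut in about 65-99% of T4a failures, and 2 or more DLTs fall by Day 21 in about 29-87% (61-68% with even onset). The net excess over Q2W is unknown: 0 to 0.47 DLTs if Q2W lowers the rate by 0 to 10 points.

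The point is minor. It arises only if T1a to T3a pass and T4a fails, and it involves at most 6 patients. In the protocol, the tremelimumab arm has no RP2D objective (Section 5.2.1) and no Part B cohort (Section 6.2).

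**What to change.** In both the synopsis table and Table JSCC.2, label the 100 mg Days 1, 8 and 15 row T4b with footnote b, and the 100 mg Q2W row T4c without it.

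If the sponsor prefers to state the condition by schedule in Section 7.2.2.2, that edit alone is not enough. Footnote b would still name the Tnb cohort and so contradict the new text at T4b. The footnote must be reworded by schedule in both copies, and its mark placed on the T4 Days 1/8/15 row.

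The cost is a protocol amendment touching two row labels and one footnote mark in each copy. No patients are added: the maxima of 42 (tremelimumab combination) and 78 (Part A) are unchanged. On the early-DLT path the corrected tremelimumab maximum is 24 + 12 = 36.
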